### Intervention Sessions:

*Participants will be seated comfortably in a chair with armrests during both the intervention and assessment visits. The assessment and intervention tasks can also be conducted while seated in a wheelchair if need be. Skin where the tDCS electrodes will be placed will be gently cleaned using an alcohol swab and hair will be separated and clipped to allow the electrode to be placed. Two saline-soaked t-DCS sponge electrodes (25 cm^2) will be used. The anode placed over the right cerebellar hemisphere, 1-2cm below the inion and 3-4cm lateral to the inion (Ferrucci et al., 2015; Grimaldi et al., 2016) and the cathode electrode will be placed on the right deltoid region. Electrodes will be kept in place with the neoprene/Velcro head band in the tDCS device kit. The device will be programmed for "real" or "sham" setting for a 20-minute duration using the setting buttons on the device. If the device is programmed for "real" tDCS, the intensity will gradually increase over the first 30-45 seconds to the designated value of 2mA and remain at that setting until it gradually decreases in intensity over the last 30-45 seconds of the 20-minute duration. If "sham" is selected, the gradual ramp up occurs followed by the ramp down. Therefore, no stimulation is provided during sham condition. While the PI is placing the electrodes, the graduate intern will be setting up the behavioral language activity (CILT) for the session. Once the electrodes are in place, the device is programmed and the behavioral activity is set up, the intervention will begin. The tDCS device will be turned on (to either real or sham) and the participant will engage in the*

## MEDICAL PROTOCOL (HRP-590)

PROTOCOL TITLE: Combining cerebellar tDCS and constraint-induced language therapy in non-fluent aphasia: a novel approach to target discourse

VERSION DATE: 08/09/2023

*behavioral intervention. The total intervention session will last for 45 minutes: 20 minutes of combined c-tDCS and CILT and the final 25 minutes CILT only. After each intervention phase, the participant will be asked to complete a short adverse effects survey which will help the research team make modifications for a larger clinical trial. The research team ran a trial intervention session with one of the members of the research team who provides responses similar to that we would expect of an individual with non-fluent aphasia. The intervention session lasted 60 minutes including placing and removing of electrodes. All members of the research team will be trained in the methods of placing electrodes and demonstrate competence. However, for this study, the PI will do all of the electrode placement. The placement of the electrodes for cerebellar stimulation is well described in the literature. For a larger clinical trial, inter-rater reliability for electrode placement will be done in order to ensure consistency among research staff.*

### 5.3. Study Duration:

*Each intervention session will be scheduled for 60 minutes to allow for set up, take down and questions from the participant. Each condition (Sham and Real tDCS) will consist of 6 intervention visits (3x/week across 2 weeks) with a 4-week washout period between conditions. After the washout period, the participant will then engage in 6 intervention visits of the opposite intervention. The intervention visits do not have to be consecutive within the intervention week.*

*The total duration of participant participation will be 17 visits across 2 months. The duration anticipated to enroll all study participants is expected to be 18 months. It is anticipated that it will take 36 months to complete all study procedures including data analysis.*

### 5.4. Individually Identifiable Health Information:

*Name, date of birth, medical diagnosis (cortical stroke) and communication diagnosis (type of aphasia) will be collected from the participant and records provided by the participant (specifically, the speech-language pathologist report).*

### 5.5. Use of radiation: N/A

### 5.6. Use of Center for Magnetic Resonance Research: N/A

## MEDICAL PROTOCOL (HRP-590)

PROTOCOL TITLE: Combining cerebellar tDCS and constraint-induced language therapy in non-fluent aphasia: a novel approach to target discourse

VERSION DATE: 08/09/2023

### **6. Data and Specimen Banking**

6.1. Storage and Access: N/A

6.2. Data: N/A

6.3. Release/Sharing: N/A

### **7. Sharing of Results with Participants**

7.1. Sharing Results: A brief summary of study results will be shared with each participant upon completion of the study along with a “Thank you” note for their participation (See thank you letter in supplemental documents).

7.2. Sharing Genetic Results: N/A

7.2.1 Disclosure of Results: N/A

7.2.2 Returning Results to Participants: N/A

Aggregate or individual results: N/A

Laboratory results: N/A

Plan for return of results to participants: N/A

Types of results to be returned to participants: N/A

7.2.3 Future analysis of genotypes: N/A

### **8. Study Population**

8.1. Inclusion Criteria:

*Eligible participants must be over the age of 18 years, have a history of stroke and diagnosed with non-fluent aphasia. The individual can provide documentation of aphasia in the form of a physician or clinician report. If they do not have documentation of their aphasia diagnosis, we will either obtain a consent from the interested participant to request the speech-language pathology assessment report, the PI can conduct an informal language assessment to confirm the diagnosis. Or, if it still unclear,*

## MEDICAL PROTOCOL (HRP-590)

PROTOCOL TITLE: Combining cerebellar tDCS and constraint-induced language therapy in non-fluent aphasia: a novel approach to target discourse

VERSION DATE: 08/09/2023

*the PI will administer the Western Aphasia Battery Assessment to determine the type and severity of aphasia.*

*In addition, eligible participants must be able to independently understand simple directions, use some speech to communicate, have access to reliable transportation (including taxi and/or other transportation services), fluent in English.*

### 8.2. Exclusion Criteria:

*Pregnancy, history of seizures within the past 12 months, any metal implants in the body such as pacemaker, cochlear implant, aneurysm coil or clip (excluding dental fillings), , psoriasis or eczema affecting the scalp, history of a head injury such as a concussion or diagnosis of a mental health or neurological condition/disease.*

### 8.3. Screening:

*The screening process will involve the research staff asking screening questions of the potential participant (screening form is in supplemental documents). This can be done either by phone, virtual visit or in-person (screening phone script is in supplemental documents). If the individual does not have documentation of an aphasia diagnosis, the PI, who is a licensed, certified and experienced speech-language pathologist will conduct an informal assessment through conversation and simple language tasks to ensure the diagnosis of non-fluent aphasia. If the diagnosis is still unclear, the PI will conduct the Western Aphasia Battery either through an in-person visit or via virtual visit to confirm the diagnosis of non-fluent aphasia. If the research staff member is a graduate student, they will be supervised by the PI, who is a licensed and certified speech-language pathologist. Graduate students in speech-language pathology programs are qualified to administer and interpret this test under the supervision/guidance of a licensed, certified speech-language pathologist. If the participant is within child-bearing years, a urine pregnancy test will be provided during the first in-person visit prior to consenting.*

## 9. Vulnerable Populations

### 9.1. Vulnerable Populations:

**MEDICAL PROTOCOL (HRP-590)**

**PROTOCOL TITLE:** Combining cerebellar tDCS and constraint-induced language therapy in non-fluent aphasia: a novel approach to target discourse

**VERSION DATE:** 08/09/2023

Population / Group	Identify whether any of the following populations will be the focus of the research (targeted), included but not the focus of the research excluded from participation in the study.
Children	Excluded
Pregnant women/fetuses/neonates	Excluded
Prisoners	
Adults lacking capacity to consent and/or adults with diminished capacity to consent, including, but not limited to, those with acute medical conditions, psychiatric disorders, neurologic disorders, developmental disorders, and behavioral disorders	
Non-English speakers	
Those unable to read (illiterate)	
Employees of the researcher	
Students of the researcher	
Undervalued or disenfranchised social group	
Active members of the military (service members), DoD personnel (including civilian employees)	
Individual or group that is approached for participation in research during a stressful situation such as emergency room setting, childbirth (labor), etc.	
Individual or group that is disadvantaged in the distribution of social goods and services such as income, housing, or healthcare.	

**MEDICAL PROTOCOL (HRP-590)**

**PROTOCOL TITLE:** Combining cerebellar tDCS and constraint-induced language therapy in non-fluent aphasia: a novel approach to target discourse

**VERSION DATE:** 08/09/2023

Individual or group with a serious health condition for which there are no satisfactory standard treatments.	
Individual or group with a fear of negative consequences for not participating in the research (e.g. institutionalization, deportation, disclosure of stigmatizing behavior).	
Any other circumstance/dynamic that could increase vulnerability to coercion or exploitation that might influence consent to research or decision to continue in research.	

9.2. Additional safeguards, if any, to ensure inclusion is appropriate:

**Active members of the military (service members), DoD personnel (including civilian employees)**: Members of the military may not be known, research staff will not be asking a direct question about military status to potential participants. We do not anticipate vulnerability for this group to be increased by participating in this study.

**Undervalued or disadvantaged social group**: Undervalued or disadvantaged people may not be known, research staff will not be asking a direct question about socioeconomic status to potential participants. We do not anticipate vulnerability for this group to be increased by participating in this study.

**Individual or group that is disadvantaged in the distribution of social goods and services such as income, housing, or healthcare**: Undervalued or disadvantaged people may not be known, research staff will not be asking a direct question about socioeconomic status to potential participants. However, we have taken special precaution to make sure participants are fairly and adequately compensated for their time in this study, yet not coerced by unreasonably high compensation amounts.

## MEDICAL PROTOCOL (HRP-590)

PROTOCOL TITLE: Combining cerebellar tDCS and constraint-induced language therapy in non-fluent aphasia: a novel approach to target discourse

VERSION DATE: 08/09/2023

9.3. If research holds prospect for direct benefit to participants, provide justification for any exclusions indicated in the table above:

*Effects of any non-invasive brain stimulation technique on an unborn infant is unknown, therefore women who are pregnant are excluded from any study involving these techniques. In order to complete the language and working memory tasks required, individuals must be fluent in English and be able to read. There are currently no normative data for these tasks in other languages. Individuals with serious health conditions will be excluded from the pilot due to the number of visits required for the study as individuals from this group may not be able to consistently attend and/or complete the required number of visits. However, a larger clinical trial could offer the intervention sessions in the individual's home, requiring the participants to only come in for the data collection/assessment sessions. At that time, this population will not be excluded.*

## 10. Local Number of Participants

10.1. Local Number of Participants to be Consented: *A total of 5 participants will be enrolled with the goal of 3 participants to complete the duration of this pilot study.*

## 11. Local Recruitment Methods

11.1. Recruitment Process:

*Paper flyers will be available in the Robert F. Pierce (RFP) Speech-Language and Hearing Clinic on the UMD campus. In addition, a poster of the flyer will be posted in the lobby of the clinic. The flyers (and poster) will have contact information for the research team, both email and phone. Interested individuals can contact the research staff for more information. The research staff will also request permission from the client to come into one of their speech-language therapy sessions at RFP to talk with them about the study to gauge their interest.*

*Flyers (paper and digital) will also be shared with local support groups, speech-language pathologists working in medical settings who are alumni of the UMD master's program, local medical community and other sources including speech-language pathology community platforms. The research team will reach out to local stroke support groups to inform them of the study and request to attend a meeting to share information about the study with members of the support group.*

## MEDICAL PROTOCOL (HRP-590)

PROTOCOL TITLE: Combining cerebellar tDCS and constraint-induced language therapy in non-fluent aphasia: a novel approach to target discourse

VERSION DATE: 08/09/2023

*To minimize attrition, a "Welcome Packet" will be provided to each participant including an individual schedule of each visit, contact information for the research staff, transportation scheduling information (if needed). Research staff will offer to assist in making transportation arrangements if needed. Weekend and evening visits can be scheduled to accommodate the participants' schedules as some may need to have a caregiver attend the sessions with them due to physical limitations, inability to drive, etc. The participant will be asked their preference re: communicating with the research team. The team will then provide regular updates and reminders through that preferred communication method (phone, text, email). During the intervention phases, the research team will be in daily contact with the participant to check in, confirm transportation and answer questions.*

*If the participant is already an RFP client, the study visits will take the place of their regularly scheduled clinic visits at RFP. Breaks will be offered both during assessment/data collection days and intervention days as needed with the exception of the tDCS application. Once the stimulation begins, ideally it should be provided without a break for that 20 minutes. If an individual expresses discomfort, additional saline solution is applied to the electrodes. If the individual continues to express discomfort, the tDCS will stop. The research team does not anticipate this as very few adverse effects have been reported using tDCS. Bottled water and light cookies/crackers will be available to the participant.*

### 11.2. Identification of Potential Participants:

*Interested individuals will contact research staff either through email or phone. Or, in person, if they are clients in the RFP Clinic.*

### 11.3. Recruitment Materials:

*Potential participants will be recruited through the Robert F. Pierce Speech-Language and Hearing Clinic on the UMD campus and surrounding communities including stroke support groups and public advertisements using paper and digital flyers. Digital flyers will also be used as posts to the Neural Function and Recovery Lab research lab social media page(s) and the lab website. Past and current clients of the RFP Speech-Language and Hearing Clinic, with a diagnosis of non-fluent aphasia, will be sent a paper flyer in the mail and will be informed of the study by their current graduate student clinician. In addition, paper flyers will be posted in the lobby of the Robert F. Pierce Speech-Language and Hearing Clinic.*

## MEDICAL PROTOCOL (HRP-590)

PROTOCOL TITLE: Combining cerebellar tDCS and constraint-induced language therapy in non-fluent aphasia: a novel approach to target discourse

VERSION DATE: 08/09/2023

### 11.4. Payment:

*Participants will receive \$150 at the end of the first intervention phase, another \$150 at the end of the second intervention phase and a \$150 bonus for completion of the study. Participants will be required to sign a log each time payment is received. Payment will be in the form of adding money to a ClingCard given to the participant.*

## 12. Withdrawal of Participants

### 12.1. Withdrawal Circumstances:

*Participants are free to withdraw from participation in the study at any time upon request. An investigator may discontinue or withdraw a participant from the study for the following reasons:*

- *Pregnancy*
- *Significant study non-compliance*
- *If any clinical adverse event (AE) or other medical condition or situation occurs such that continued participation in the study would not be in the best interest of the participant*
- *If the participant meets an exclusion criterion (either newly developed or not previously recognized) that precludes further study participation*

### 12.2. Withdrawal Procedures:

*If a participant wishes to withdraw or we determine that the participant should withdraw, we will terminate data collection and discuss with the participant the reasons for withdrawal. All data collected up to that point will be used in analysis unless the participant wishes for their data not to be used.*

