### 1. Objectives

#### 1.1. Purpose:

*To determine the effect of combining constraint-induced language therapy (CILT) with cerebellar tDCS in individuals with non-fluent aphasia after stroke.*

*The primary aims are to 1) determine the effect of combining cerebellar tDCS with constraint-induced language therapy (CILT) on language as measured by a verbal fluency task and discourse analysis task in a prospective, crossover study of adults with non-fluent aphasia after a cortical stroke and 2) demonstrate feasibility and data collection to inform a larger study.*

*The secondary aims include impact of the combined intervention on 1) resting state spectral EEG as measured through delta wave percentage 2) working memory as measured by the score on the Wisconsin Card Sorting Test and 3) quality of life as measured by the Stroke Aphasia Quality of Life survey tool. A final secondary aim will be to identify the tolerance of the intervention and barriers to participation measured by the adverse events questionnaire.*

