## MEDICAL PROTOCOL (HRP-590)

PROTOCOL TITLE: Combining cerebellar tDCS and constraint-induced language therapy in non-fluent aphasia: a novel approach to target discourse

VERSION DATE: 08/09/2023

4. An adverse events/experiential survey will be given to participants to provide using a Likert Scale 1-4. In addition two open ended questions will be asked about positive experiences and negative experiences to help us identify barriers to participation. The objective portion will provide us a raw score and the open ended questions will be analyzed qualitatively for agreement and themes. This information will be used to hone the methodology to improve retention and reduce attrition in a larger clinical trial. This survey will be provided at the end of the experience. If a participant drops out, the research team will reach out to ask the participant to complete the survey to assist us in establishing better methodology.

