## MEDICAL PROTOCOL (HRP-590)

PROTOCOL TITLE: Combining cerebellar tDCS and constraint-induced language therapy in non-fluent aphasia: a novel approach to target discourse

VERSION DATE: 08/09/2023

more information and later be upgraded to “probably related” or “definitely related”, as appropriate.

- **Unlikely to be related:** A clinical event, including an abnormal laboratory test result, whose temporal relationship to study intervention administration makes a causal relationship improbable (e.g., the event did not occur within a reasonable time after administration of the study intervention) and in which other drugs or chemicals or underlying disease provides plausible explanations (e.g., the participant’s clinical condition, other concomitant treatments).
- **Not Related:** The AE is completely independent of study intervention administration, and/or evidence exists that the event is definitely related to another etiology. There must be an alternative, definitive etiology documented by the clinician.

**Expectedness:** The Investigator will be responsible for determining whether an adverse event is expected or unexpected. An adverse event will be considered unexpected if the nature, severity, or frequency of the event is not consistent with the risk information previously described for the study intervention.

**Reporting of adverse events:** Information on all adverse events will be collected including the:

- Event description
- Time of onset
- Assessment of severity
- Relationship to study intervention
- expectedness
- Time of resolution/stabilization of the event

All adverse events occurring while on study will be documented appropriately regardless of relationship. All adverse events will be followed to adequate resolution.

Any medical condition that is present at the time that the participant is screened will be considered as baseline and not reported as an adverse event. However, if the participant’s condition deteriorates at any time during the study, it will be recorded as an adverse event.

The investigator will record all reportable events with start dates occurring any time after informed consent is obtained until 7 (for non-serious adverse events) or 30 days (for serious adverse events) after the last day of study participation. At each study visit,

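### Section 12.2 stops all data collection at withdrawal, which conflicts with the drop-out survey in 3.2 and adverse event follow-up in 18.2, and its analysis opt-out makes no exception for safety or disposition data

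*Combined protocol and SAP*

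**What the plan says.** Section 12.2 covers withdrawal by the participant and by the investigator. In either case "we will terminate data collection and discuss with the participant the reasons for withdrawal". On data already held it adds: "All data collected up to that point will be used in analysis unless the participant wishes for their data not to be used". Neither sentence separates outcome data from safety or disposition data.

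Section 12.1 lists the reasons for withdrawal by the investigator, and one begins "If any clinical adverse event (AE) or other medical condition or situation occurs". The stop in 12.2 therefore applies to people withdrawn because of an adverse event.

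Two other sections provide for collection after a participant leaves:

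- Section 3.2 item 4, on the adverse events/experiential survey: "If a participant drops out, the research team will reach out to ask the participant to complete the survey".
- Section 18.2: "All adverse events will be followed to adequate resolution". It also has reportable events recorded "until 7 (for non-serious adverse events) or 30 days (for serious adverse events) after the last day of study participation".

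Section 1.1 makes feasibility a primary aim and states: "A final secondary aim will be to identify the tolerance of the intervention and barriers to participation measured by the adverse events questionnaire". Section 15.3 reports attrition and adverse events descriptively, as counts and rates. It gives no denominator and no rule for participants who leave.

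**The concern.** Staff dealing with a withdrawal have two sets of instructions that cannot both be followed as written. Under 12.2 nothing more is collected. Under 3.2 and 18.2 a survey is requested, open adverse events are followed, and new ones are recorded for a fixed period. The conflict is sharpest for someone withdrawn because of an adverse event, who falls under both rules on the same day.

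The opt-out is a separate gap. A leaver may ask that earlier data not be used, and as written this reaches adverse event and disposition data as well as language scores. The tolerance aim and the planning of a larger trial depend on what leavers experienced and why they left, which completers cannot supply. If the data from leavers with events go missing, the intervention looks better tolerated than it was.

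**Working it through.** The plan states no figure on this point, so there is none to reproduce. The check is a comparison of the sections, followed by a small illustration of size.

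**Step 1. The rules side by side.**

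| Item | 12.2 | 3.2 item 4 | 18.2 |
|---|---|---|---|
| Survey after leaving | Collection stops | Team contacts the leaver and asks | Not addressed |
| Open adverse event | Collection stops | Not addressed | Followed until resolved |
| New event after leaving | Collection stops | Not addressed | Recorded for 7 or 30 days |
| Data already held | Used unless the participant objects | Not addressed | All events documented, related or not |

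For a leaver, the natural reading of the last day of participation is the day of withdrawal. On that reading the 7/30-day window in 18.2 opens at the moment 12.2 closes collection. In addition, the routine enquiry in 18.2 is made at study visits, and a leaver has no more of them.

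**Step 2. Planned size.** Section 10.1 enrols 5 with a goal of 3 completers. Planned non-completers: 5 − 3 = 2, and 2/5 = 40%. This is a planning figure, not an upper limit.

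**Step 3. What one record does to a rate.** The documents give no expected event rate, so these cases are assumptions. Rate = participants with an event / participants counted. The 95% intervals are exact (Clopper-Pearson); with no events the upper limit is 1 − 0.025^(1/n), for example 1 − 0.025^(1/4) = 0.602.

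| Assumed situation | All 5 kept | Opted-out leavers excluded |
|---|---|---|
| One leaver had an event and opts out; nobody else had one | 1/5 = 20% (1% to 72%) | 0/4 = 0% (0% to 60%) |
| Both leavers had events and opt out; no completer had one | 2/5 = 40% (5% to 85%) | 0/3 = 0% (0% to 71%) |
| One leaver without an event opts out; one other participant had one | 1/5 = 20% (1% to 72%) | 1/4 = 25% (1% to 81%) |

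The first row is the modest case and the second an extreme one. The third shows that the direction depends on who opts out: the rate is understated when the excluded leaver had an event and slightly overstated when not. The intervals are wide throughout, so the statistical information in any such rate is limited. The practical point is that a single record decides whether an event is reported at all.

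**The case against.** The strongest reply is that the sections can be read together. On that reading 12.2 ends scheduled study data, while the more specific text in 3.2 and 18.2 governs the survey and adverse events. All data are collected in one laboratory under one investigator, so different sites cannot apply different readings. Much is also on file before anyone leaves: "After each intervention phase, the participant will be asked to complete a short adverse effects survey" (section 5.2), Table 1 lists adverse events during intervention and at follow-up, 18.2 has them asked about at each visit, and 12.2 itself has the reasons for withdrawal discussed and keeps earlier data by default.

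Most of this stands, and it rules out three stronger readings that a reader might infer:

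- That leavers' safety and tolerance data will be lost. Loss follows only if 12.2 is applied literally or a leaver opts out. Section 3.2 also obliges the team only to ask, so some leavers may decline the survey under any wording.
- That up to 40% of participants would give no survey and no adverse event follow-up. Someone who leaves after the first phase may already have a survey on file, and 3 completers is a goal, so 40% is not a ceiling.
- That the opt-out deletes adverse event records. It removes data from analysis. It does not cancel the 18.2 duty to document events or the reporting duties to the IRB, and nothing in 12.2 says that a leaver vanishes from the attrition count.

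The reply does not remove the conflict. The combined reading is sensible, but no section states it. Nor does it answer the opt-out, which has no exception for the quantities reported under 15.3.

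**Conclusion.** The point holds as a conflict between sections plus an unqualified opt-out. The unconditional stop in 12.2 contradicts the post-withdrawal collection in 3.2 item 4 and 18.2, and the document does not say which prevails. Post-withdrawal tolerance and safety data may be lost if 12.2 is followed to the letter, and adverse event rates may be understated if a leaver who had an event opts out.

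The comparison of sections needs no assumption beyond taking a leaver's last day of participation to be the day of withdrawal. The size rests on assumed events: the shift from 20% to 0% needs one leaver to have the only event and to opt out. The shift from 40% to 0% needs both leavers to have events, no completer to have one, and both leavers to opt out; nothing in the documents makes that combination likely.

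The consent form and standard operating procedures are not part of the document, so whether they already settle the matter cannot be judged. The amendment is worth making before a withdrawal forces staff to choose between the rules. The point does not concern the language outcomes or the power statement.

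**What to change.** Reconcile 12.2 with 3.2 and 18.2:

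1. Limit the stop on data collection to intervention and outcome-assessment visits.
2. State that, unless the participant refuses contact, the survey request in 3.2 item 4 and the adverse event follow-up and recording already set out in 18.2 continue after withdrawal.
3. State that the opt-out applies to outcome data, and that de-identified adverse event and disposition records stay in the 15.3 counts and rates.
4. In 15.3, name all enrolled participants as the denominator and report how many opted out.

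This relies on follow-up rules that the protocol already contains and adds no clinical rule. The cost is a short amendment, plus contact with each leaver that 3.2 and 18.2 already imply. The downside is a slightly narrower opt-out for participants. That is a policy choice, so it needs matching consent wording and IRB agreement.
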